### **3. INVESTIGATIONAL PLAN**

#### **3.1. Study Design**

This is a randomised, parallel group, multi-centre, open-label Phase II study in subjects with HER2-positive metastatic breast cancer which has progressed following prior therapy, which must have included anthracyclines and taxanes and therapy with trastuzumab in the metastatic setting. This study is not placebo controlled, and there is no active comparator.

Protocol waivers or exemptions are not allowed with the exception of immediate safety concerns. Therefore, adherence to the study design requirements, including those specified in the Time and Events Schedule ([Table 16](#), and [Table 17](#)), is essential and required for study conduct.

Supplementary study conduct information not mandated to be present in this protocol is provided in the accompanying SPM. The SPM will provide the site personnel with administrative and detailed technical information that does not impact subject safety.

Subjects must be screened for eligibility and informed consent must be given before any study-related procedures are conducted.

All subjects will receive treatment with lapatinib 1250mg once daily and capecitabine 1000mg/m^2 twice daily until disease progression. Lapatinib will be given every day; capecitabine will be given in 3 week cycles of two weeks treatment followed by one week off treatment.

Subjects will be randomised in a 1:1 ratio to receive either:

- Octreotide (Sandostatin LAR) 40mg 7 days before the start of treatment with lapatinib and capecitabine and again 28 days later, or
- No octreotide treatment.

For subjects randomised to receive octreotide, treatment with lapatinib and capecitabine will be initiated 7 days after the first dose of octreotide given as the LAR formulation. For subjects randomised to receive no octreotide, treatment with lapatinib and capecitabine will be initiated immediately following enrolment.

Subjects randomised to receive octreotide LAR must be given one 0.1mg dose of the standard formulation of octreotide s.c. to assess tolerability at least one hour before the first dose of the LAR formulation is administered. Subjects with significant intolerance to octreotide 0.1mg s.c. will not receive treatment with octreotide LAR, but will receive treatment with lapatinib and capecitabine as scheduled.

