### **4.3. Permanent Discontinuation from Study Treatment and Subject Completion Criteria**

#### **4.3.1. Discontinuation from Treatment with Octreotide**

Subjects randomised to receive octreotide must be given one 0.1mg dose of the standard formulation of octreotide s.c. to assess tolerability at least one hour before the first dose of the LAR formulation is administered. Subjects who show any evidence of intolerability to octreotide administered s.c. **must not** receive treatment with the LAR formulation; these subjects should receive treatment with lapatinib and capecitabine and should not be withdrawn from the study.

Subjects randomised to receive octreotide will be given prophylactic octreotide (Sandostatin LAR) 40mg 7 days before the start of treatment with lapatinib and capecitabine and again 28 days later. Episodes of mild diarrhoea which occur following treatment with octreotide LAR should be managed in accordance with the diarrhoea management guidelines ([Appendix 1](#)). The use of octreotide in the s.c. formulation for the management of diarrhoea refractory to treatment with loperamide is not excluded. Investigators should use their clinical judgement concerning the use of octreotide s.c. in

subjects randomised to receive treatment with octreotide LAR, particularly during Week 2 through to Week 12 of treatment with lapatinib and capecitabine, when circulating concentrations of octreotide should already be within the clinically effective range. Subjects who report constipation with a severity of NCI CTCAE Grade 2 and above (Table 9) or other adverse events which are considered likely to be related to octreotide treatment following the first dose of octreotide LAR must not receive the second dose of octreotide LAR, but should continue to receive lapatinib and capecitabine and should not be withdrawn from the study.

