#### **5.3.1. Octreotide Dosage and Administration**

Octreotide in the formulation for s.c. injection will be administered as a 0.1mg dose (1mL) at the study site to assess tolerability at least one hour before the first 40mg dose of the LAR formulation is administered. The LAR formulation must not be administered to any subjects who show signs or symptoms of intolerance to octreotide following administration of the 0.1mg s.c. dose.

The 40mg dose of the LAR formulation will be given as two 20mg doses, each of approximately 2.5mL. The mixing instructions for this formulation should be followed carefully to ensure the suspension is properly prepared. Octreotide in the LAR formulation will be administered at the study site 7 days prior to starting the first cycle of treatment with lapatinib and capecitabine, and repeated 28 days later.

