## 5.9. Dose Adjustment

Dose adjustment will be considered for lapatinib (Section 5.10) and capecitabine (Section 5.11), and the dose of either agent may be adjusted independently of the other. All subjects who may require discontinuation of either lapatinib or capecitabine must discontinue both treatments. Subjects should be carefully instructed when any dose modifications occur.

Treatment with lapatinib and capecitabine may be delayed up to 2 weeks, to allow for resolution of toxicity except in the event of a  $\geq$  Grade 3 relative decrease in left ventricular ejection fraction, interstitial pneumonitis or hepatotoxicity. Guidelines for the management of these events are presented in Section 5.12.3 (cardiovascular and respiratory) and Section 5.13 (hepatobiliary).

No dose reduction or dose delay is permitted for octreotide. Subjects who show intolerance to the s.c. injection of octreotide must not receive treatment with octreotide LAR. Episodes of mild diarrhoea which occur following the first dose of octreotide LAR and prior to the first dose of lapatinib and capecitabine should be managed in accordance with the diarrhoea management guidelines (Appendix 1). The use of octreotide in the s.c. formulation for the management of diarrhoea refractory to treatment with loperamide is not excluded. Investigators should use their clinical judgement concerning the use of octreotide s.c. in subjects randomised to receive treatment with octreotide LAR, particularly during Week 2 through to Week 12 of treatment with lapatinib and capecitabine, when circulating concentrations of octreotide should already be within the clinically effective range.

Subjects who report constipation with a severity of NCI CTCAE Grade 2 and above (Table 9) or other adverse events which are considered likely to be related to octreotide treatment following the first dose of octreotide LAR must not receive the second dose of octreotide LAR.

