### 7.1.4. Post-Randomisation

Subjects will be randomised to receive octreotide or to receive no octreotide.

For subjects randomised to receive octreotide:

- Administer the octreotide 0.1mg s.c. tolerability assessment dose, monitor for at least one hour and record any AEs associated with this dose.
- Administer first dose of octreotide 40mg LAR (only in subjects who have not shown intolerance to the octreotide 0.1mg s.c. tolerability assessment dose).

For subjects randomised to receive no octreotide:

- Dispense lapatinib and capecitabine to the subject with instructions for taking therapy.

All subjects will be given advice concerning the management of diarrhoea. It is recommended that subjects should be provided with loperamide for the prompt management of diarrhoea.

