## 9.3. Data Analysis Considerations

### 9.3.1. Analysis Populations

The Intent-to-Treat (ITT) population will comprise all randomised subjects regardless of whether or not treatment was administered. This population will be based on the treatment to which the subject was randomised. Any subject who receives a treatment randomisation number will be considered to have been randomised. The primary analysis of disease efficacy and all diarrhoea-related efficacy endpoints will be conducted using the ITT population.

The modified ITT (m-ITT) population will comprise all subjects in the ITT population who do not show intolerance to octreotide in the s.c. formulation and who do not have diarrhoea recorded as an AE after the first dose of octreotide LAR and prior to the start of treatment with lapatinib and capecitabine. The supplementary analysis of all diarrhoea-related efficacy endpoints will be conducted using the m-ITT population.

The Per-Protocol (PP) population will comprise all randomised subjects who receive at least one dose of study treatment and who comply closely with the protocol. Major protocol violations that would exclude subjects from the PP population will be defined and documented in the Reporting and Analysis Plan (RAP) prior to database release. The PP population will not be analysed if this population comprises more than 95% of the ITT population.

The Safety population will comprise all randomised subjects who receive at least one dose of study treatment and will be based on the actual treatment received if this differs from that to which the subject was randomised. This population will be used for the analysis of clinical safety data.

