2.2 Analysis Populations

Intent-to-Treat Population

The Intent-to-Treat (ITT) population will comprise all randomised subjects regardless of whether or not treatment was administered. This population will be based on the treatment to which the subject was randomised. Any subject who receives a treatment randomization number will be considered to have been randomised. The primary analysis of disease efficacy and all diarrhoea-related efficacy endpoints will be analysed using the ITT population.

Modified ITT

The modified ITT (m-ITT) population will comprise all subjects in the ITT population and under Octreotide arm this population will include subjects who do not show intolerance to octreotide in the s.c. formulation and who do not have non treatment related diarrhoea recorded

as an AE after the first dose of octreotide LAR and prior to the start of treatment with lapatinib and capecitabine. A sensitivity analysis of diarrhoea-related primary efficacy endpoint will be conducted using the m-ITT population.

Per Protocol Population

The Per-Protocol (PP) population will comprise all randomised subjects who receive at least one dose of study treatment and who comply closely with the protocol (that is subjects who are not excluded from PP set as per PDMP). The PP population will not be analysed if this population comprises more than 95% or less than 50% of the ITT population. The analysis of primary efficacy endpoint will be repeated using the PP population.

Subjects with potential PDs will be excluded from PP population based on Protocol Deviation Management Plan (PDMP).

Safety Population

The Safety population will comprise all randomised subjects who receive at least one dose of study treatment and will be based on the actual treatment received if this differs from that to which the subject was randomised. This population will be used for the analysis of clinical safety data. Moreover, if a subject who was randomised to Octreotide arm, showed intolerance to octreotide in the s.c. formulation, and took at least one dose of lapatinib or capecitabine, then subject will be included in no Octreotide arm for safety analysis.

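### Octreotide LAR is withheld under differing, undefined test-dose thresholds, and SAP 2.2 moves subjects who showed intolerance to the no-octreotide safety arm without requiring that LAR was withheld

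*Protocol*

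**What the plan says.** **Dosing.** Every subject randomised to octreotide first receives a 0.1 mg s.c. test dose, and the response decides whether LAR may follow. The threshold is worded in several ways:

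- Protocol Summary, Protocol 3.1 and SAP 1.1: "Subjects with significant intolerance to octreotide 0.1mg s.c. will not receive treatment with octreotide LAR".
- Protocol 4.3.1: "Subjects who show any evidence of intolerability to octreotide administered s.c" must not be given LAR.
- Protocol 5.3.1: "The LAR formulation must not be administered to any subjects who show signs or symptoms of intolerance to octreotide".
- Protocol 5.9: "Subjects who show intolerance to the s.c. injection of octreotide must not receive treatment with octreotide LAR".
- Protocol 7.1.4: LAR is given "only in subjects who have not shown intolerance to the octreotide 0.1mg s.c. tolerability assessment dose".

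No section grades or defines intolerance, or says what makes it significant. By contrast, the constipation rule for withholding the second LAR dose has a CTCAE grade attached (Protocol 3.1, Table 9).

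**Analysis.** Protocol 9.3.1 limits m-ITT to subjects "who do not show intolerance to octreotide in the s.c. formulation and who do not have diarrhoea recorded as an AE" between the first LAR dose and the start of lapatinib and capecitabine. SAP 2.2 keeps the same trigger: "under Octreotide arm this population will include subjects who do not show intolerance to octreotide in the s.c. formulation". For the Safety population, SAP 2.2 first says that subjects are analysed by the treatment they actually received. It then adds a rule for anyone randomised to octreotide who meets this condition: "showed intolerance to octreotide in the s.c. formulation, and took at least one dose of lapatinib or capecitabine, then subject will be included in no". The words that follow name the arm without octreotide as her place in the safety tables.

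**The concern.** After a mild reaction to the test dose, LAR may follow under Protocol 3.1 and may not under 4.3.1 or 5.3.1. A site cannot comply with both, and the same act can be compliant or a treatment deviation depending on which section is applied. That judgement feeds the deviation categories in SAP 2.3.2 and may affect per-protocol membership.

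The statistical consequence lies in SAP 2.2. The Safety reassignment is triggered by the reaction to the test dose, not by whether LAR was given. If the two part company, a subject exposed to LAR is counted in the Lap+Cap column together with any adverse events that LAR causes. The safety comparison would then be contaminated in the direction that hides octreotide toxicity, and safety and tolerability is a stated secondary objective retained in SAP Table 1-3. The same undefined word removes her from m-ITT.

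**Working it through.** No stated figure in the plan depends on this point, so the check is mainly a comparison of texts.

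**Step 1: follow an octreotide-arm subject through the rules.** Assume that she goes on to take lapatinib or capecitabine.

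| Reaction to test dose | Dosing text followed | LAR given | Safety column, actual-treatment rule | Safety column, reassignment sentence | m-ITT |
|---|---|---|---|---|---|
| None | any | yes | octreotide | octreotide | in, if no early diarrhoea AE |
| Lesser intolerance | 3.1, SAP 1.1 | yes | octreotide | **no octreotide** | out |
| Lesser intolerance | 4.3.1, 5.3.1, 5.9, 7.1.4 | no | turns on whether the test dose counts | no octreotide | out |
| Significant intolerance | any | no | turns on whether the test dose counts | no octreotide | out |

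In the second row two adjacent sentences of SAP 2.2 give opposite answers for the same subject. The SAP's own dosing summary in 1.1 is what makes that row possible.

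**Step 2: the subject correctly denied LAR.** She has still had 0.1 mg of s.c. octreotide. SAP 2.1.3.2 starts the safety clock at the first dose of octreotide, lapatinib or capecitabine, so any adverse event after the test dose would appear in the no-octreotide column once she is reassigned.

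**Step 3: size, as illustration only.** The documents give no rate of intolerance to the test dose. SAP section 1 reports 62 enrolled at the interim. With 1:1 allocation I assume 62 / 2 = 31 per arm, all in the Safety population. If k LAR-treated subjects meet the reassignment trigger, the columns become 31 − k and 31 + k, and the LAR-treated share of the no-octreotide column is k / (31 + k):

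| k | octreotide / no octreotide | share at 31 per arm | share at the planned 70 per arm, k / (70 + k) |
|---|---|---|---|
| 1 | 30 / 32 | 1/32 = 3.1% | 1/71 = 1.4% |
| 2 | 29 / 33 | 2/33 = 6.1% | 2/72 = 2.8% |
| 3 | 28 / 34 | 3/34 = 8.8% | 3/73 = 4.1% |
| 5 | 26 / 36 | 5/36 = 13.9% | 5/75 = 6.7% |

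**Step 4: the primary analysis.** ITT is by randomised arm in Protocol 9.3.1 and SAP 2.2. No version of the intolerance rule changes ITT membership or arm.

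**The case against.** Four sections that instruct sites on dosing and discontinuation (Protocol 4.3.1, 5.3.1, 5.9, 7.1.4) withhold LAR without the qualifier *significant*. That qualifier appears only in the Summary, the design overview and the SAP's copy of the overview. A site that gives LAR after lesser intolerance has acted against those four sections, so the problem subject may never have occurred. Read together with the actual-treatment sentence before it, the reassignment sentence was probably meant for subjects who failed the test dose and had no LAR. Both arguments stand as limits on how likely the error is. They do not remove it: the design section is part of the protocol, and a programmer applying the reassignment sentence as written would move the subject.

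Three stronger readings are tempting and are not supported.

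- *The SAP invented its own threshold.* A reader might infer this from SAP 2.2, but the ungraded word is the protocol's own: it governs dosing in 5.9 and 7.1.4 and m-ITT in 1.2 and 9.3.1.
- *LAR-treated subjects have been misclassified.* The documents show that the rule permits it, not that it happened.
- *The inconsistency costs power.* Withholding LAR from part of the arm could dilute the ITT effect, but one consistently applied strict rule would do the same, so the loss would not measure the inconsistency. Any figure would also need a reaction rate that the documents do not give. Protocol 1.3.1 describes gastrointestinal events as very common with octreotide treatment in general, not after a single 0.1 mg dose. Power at 70 per arm is moot in any case, because the trial stopped for futility, and SAP 2.5.4 applies no test to m-ITT.

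**Conclusion.** The point holds in this form: the test-dose wording conflicts within the protocol and between protocol sections and SAP 1.1, and the Safety reassignment in SAP 2.2 omits the one condition that would make it agree with the actual-treatment rule beside it. The wording conflict is certain. Misclassification is conditional on at least one subject having received LAR after a reaction recorded as intolerance. How many did is unknown from the documents, and the shares in the working rest on assumed counts and an assumed 31 per arm. The effect is confined to the safety tables, m-ITT membership and the judging of deviations. The primary ITT result does not move. It is still worth correcting, because the Safety and m-ITT definitions govern the final abbreviated report.

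**What to change.** 1. **Safety population, SAP 2.2.** Make the move to the no-octreotide arm conditional on the recorded fact that no octreotide LAR was administered. No LAR-treated subject can then be counted as no-octreotide. In reassigned subjects, list or flag adverse events with onset after the s.c. test dose.
2. **m-ITT, SAP 2.2.** Base the exclusion on LAR not having been given after the test dose, and record this in SAP section 4 as a change from Protocol 1.2 and 9.3.1. This needs only the fact of administration. The documents do not say that the reason for withholding LAR is captured.
3. **Test-dose criterion.** The sponsor must reconcile the Protocol Summary, Protocol 3.1, 4.3.1, 5.3.1, 5.9 and 7.1.4, and SAP 1.1 to one defined criterion, and judge protocol deviations against it. This review does not say which criterion. Because recruitment has stopped, the step no longer changes anyone's dosing.

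The cost is one condition in each of two definitions, one flag in the adverse event listing, and an entry in SAP section 4. Protocol 5.8 already has octreotide administration recorded in the eCRF, so no new data are needed for steps 1 and 2. If the database is already locked, report the change in the CSR as a deviation from the SAP, as SAP 2.1.2 provides.

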**Table 9 National Cancer Institute common terminology criteria for grading constipation adverse events**

Adverse Event Grade	Constipation
1	Occasional or intermittent symptoms; occasional use of stool softeners, laxatives, dietary modification, or enema
2	Persistent symptoms with regular use of laxatives or enemas; limiting instrumental ADL
3	Obstipation with manual evacuation indicated; limiting self care ADL
4	Life-threatening consequences; urgent intervention indicated
5	Death

ADL=Activities of daily living

Dose reductions and dose delays are permitted during treatment with lapatinib and capecitabine. The procedures to be followed are described in Section 5.10 for lapatinib and in Section 5.11 for capecitabine.

Study completion will be the end of 24 weeks treatment with lapatinib and capecitabine, or disease progression, unacceptable toxicity or subject withdrawal if this is sooner. Serious AEs and other safety data will be reported beyond 24 weeks in subjects who continue treatment with lapatinib and capecitabine until disease progression in countries where the Sponsor is supplying lapatinib and capecitabine. Serious AEs will be followed up until resolution or stabilization of the event or until the subject is lost to follow-up.

The efficacy of prophylactic octreotide in reducing the frequency and severity of diarrhoea is the primary endpoint of this study. Each episode of diarrhoea will be recorded by the investigator as an AE in the eCRF in accordance with the standard AE reporting procedure. Actions associated with the management of diarrhoea (use of anti-diarrhoeal medication, unscheduled visits to healthcare professionals, treatment interruption, rehydration) will be recorded in the eCRF.

Subjects will complete the DMD every week and the FACIT-D every 3 weeks during treatment with lapatinib and capecitabine to provide an additional perspective on the effects of treatment-associated diarrhoea.

Diarrhoea, nausea and vomiting, dermatological events, hepatobiliary, cardiovascular and respiratory events have been identified as events of special interest relating to lapatinib. Management of dermatological events, gastrointestinal events, and cardiovascular and respiratory events is described in Section 5.12.1, Section 5.12.2, and Section 5.12.3, respectively. Dose delay and dose reduction guidance for lapatinib related to these events and to hepatobiliary events is described in Section 5.10. If future changes are made to this guidance, formal documentation will be created and stored with the study file. Any changes will be communicated to the investigative sites in the form of a letter and the revised version of the AE management or dose modification guidelines will be included in the SPM.

Hand and foot syndrome has been identified as an event of special interest relating to capecitabine. Management of this event is described in further detail in Section 5.12.4. Dose delay and dose reduction guidance for capecitabine related to this event is described in Section 5.11. If future changes are made to this guidance, formal documentation will be created and stored with the study file. Any changes will be communicated to the investigative sites in the form of a letter and the revised version of the AE management or dose modification guidelines will be included in the SPM.

There are no events of special interest relating to octreotide [[Octreotide SPC](#)].

The GSK SRT will review safety data from this study on an ongoing basis. A formal review of safety data will be conducted after the first 60 subjects (approximately 30 in each treatment arm) have received at least 9 weeks of treatment with lapatinib and capecitabine; subsequent reviews will be conducted at least every 12 weeks, or more frequently if required. It is anticipated that the SRT will meet at least three times during the course of the study. There are no pre-defined stopping rules for this study.

